14.1 Table 1: Baseline characteristics before and after adjustment

Variable	Before adjustment			After adjustment		
	Referent	Exposure	Std. diff.	Referent	Exposure	Std. diff.
Number of patients			-			-
Age categories						
...						

14.2 Table 2: Follow-up time

Patient Group	Median Follow-Up Time (Days) [IQR]
Overall Patient Population	
Referent	
Exposure	

14.3 Table 3: Censoring events

	Overall	Referent	Exposure

Outcome			
Death			
Start of an additional exposure			
End of index exposure			
Specified date reached			
End of patient data			
End of patient enrollment			
...			

14.4 Table 4: Results from primary analyses;

Analysis	No. exposed events	No. referent events	Exposed rate	Referent rate	HR (95% CI)
Crude					
Analysis 1					
Analysis 2					
...					

HR, Hazard Ratio; CI, Confidence Interval.

14.5 Table 5: Results from secondary analyses;

15. References

Appendix A

#	RE-LY trial definitions	Implementation in routine care	References/Rationale	Color coding
	Trial details- Primary approval; Unintended 5 with label change		Please see the following Google Drive for further details or any missing information: https://drive.google.com/open?id=1WD618wrywYIeaXrlTcuK-Vcnb6b-g2	Criteria
	EXPOSURE vs. COMPARISON		ICD-10 codes are not listed in this document because of excel cell size limitations and excessive number of ICD-10 codes. Full ICD-10 code lists will be available in the above Google Drive Folder (link above). ICD-9 to ICD-10 code conversions were completed using a SAS macro that implements forward/ backward mapping based on the CMS ICD-9 to ICD-10 mapping: https://www.ncbi.nlm.nih.gov/pmc/articles/PMC2907330/	Adequate mapping in claims
	Fixed doses of dabigatran (110 mg or 150 mg twice daily) vs. adjusted-dose warfarin	Dabigatran (110mg or 150mg twice daily) vs adjusted-dose warfarin		Intermediate mapping in claims
	PRIMARY OUTCOME			Poor mapping or cannot be measured in claims
	The primary outcome is a composite of stroke (including hemorrhagic) and systemic embolism event	
Measured 1 day after drug initiation in diagnosis position and care setting specified below.
 
For stroke: Primary diagnosis position in inpatient care setting ICD-9: 430.xx Subarachnoid hemorrhage (SAH) ICD-10: 431.xx Intracerebral hemorrhage (ICH) ICD-9: 433.x1 Occlusion and stenosis of precerebral arteries with cerebral infarction ICD-10: 434.xx (excluding 434.x0) Occlusion and stenosis of cerebral arteries with cerebral infarction ICD-9: 436.x Acute, but ill-defined cerebrovascular events
 
Systemic embolism (Arterial embolism and thrombosis): Primary diagnosis position in inpatient care setting ICD-9: 444.xx ICD-10: 174.x
	
For stroke: PPV of 85% or higher for ischemic stroke PPV ranging from 80% to 98% for hemorrhagic stroke →[Andrade SE, Harrold LR, Tjia J, et al. A systematic review of validated methods for identifying cerebrovascular accident or transient ischemic attack using administrative data. Pharmacoepidemiology and Drug Safety 2012;21 Suppl 1:100-28.] →[Trischwell DL, Longstreth WT, Jr. Validating administrative data in stroke research. Stroke; a journal of cerebral circulation 2002;33:2465-70.] →[Roumie CL, Mitchel E, Gideon PS, Varas-Lorenzo C, Castellsague J, Griffin MR. Validation of ICD-9 codes with a high positive predictive value for incident strokes resulting in hospitalization using Medicaid health data. Pharmacoepidemiology and drug safety 2008;17:20-6.]
	Can't be measured in claims but not important for the analysis
	INCLUSION CRITERIA			
1	1 AF documented as follows: (1a or 1b or 1c)			
1a	• There is ECG documented AF on the day of screening or randomization	
Measured 4 weeks prior to and including day of drug initiation in any diagnosis position and any care setting
 
Atrial fibrillation ICD-9 diagnosis: 427.31 ICD-10 diagnosis: I48.0x, I48.1x, I48.2x, I48.9x
		
1b	• The patient has had a symptomatic episode of paroxysmal or persistent AF documented by 12-lead ECG within 6 m before randomization	
Measured 12 months prior to and including day of drug initiation in any diagnosis position and inpatient or outpatient care setting
 
Atrial fibrillation ICD-9 diagnosis: 427.31 ICD-10 diagnosis: I48.0x, I48.1x, I48.2x, I48.9x
		
1c	
• There is documentation of symptomatic or asymptomatic paroxysmal or persistent AF on 2 separate occasions, at least 1 day apart, one of which is within 6 m before randomization.
 
In this case, AF may be documented by 12 lead ECG, rhythm strip, pacemaker/ICD electrogram, or Holter ECG. The duration of AF should be at least 30 s.
 
Electrograms (not marker channels or mode switch episodes) from pacemakers and defibrillators can be used to document only 1 episode of paroxysmal or persistent AF
	
>2 Diagnoses separated by 1 day to 30 days, measured 12 months prior to and including day of drug initiation in any diagnosis position and inpatient or outpatient care setting
 
Atrial fibrillation ICD-9 diagnosis: 427.31 ICD-10 diagnosis: I48.0x, I48.1x, I48.2x, I48.9x
		
2	In addition to documented AF, patients must have one of the following: (2a or 2b or 2c or 2d or 2e)			
2a	• History of previous stroke, TIA, or systemic embolism	
Measured any time prior to and including day of drug initiation in any diagnosis position and inpatient care setting
 
Any stroke ICD-9 diagnosis: 430.xx, 431.xx, 433.xx, 434.xx, 436.xx
 
Systemic embolism ICD-9 diagnosis: 444.xx (arterial embolism) ICD-10 diagnosis: 174.x arterial embolism and thrombosis
 
TIA ICD-9 diagnosis: 435.xx (Transient cerebral ischemia)
		
2b	• Ejection fraction <40% documented by echocardiogram, radionuclide or contrast angiogram in the last 6 m	
Measured 180 days prior to and including day of drug initiation in any diagnosis position and inpatient care setting
 
Heart failure, systolic ICD-9 diagnosis: 428.2x, 428.4x ICD-10 diagnosis: I50.2x, I50.4x
		
2c	• Symptomatic heart failure, New York Heart Association class 2 or higher in the last 6 m	
Measured 180 days prior to and including day of drug initiation in any diagnosis position and inpatient care setting
 
Congestive heart failure ICD-9 diagnosis: 428.x, 398.91, 402.01, 402.11, 402.91, 404.01, 404.11, 404.91, 404.03, 404.13, 404.93 ICD-10 diagnosis: I50.1, I50.2x, I50.3x, I50.4x, I50.8x, I50.9, I09.81, I11.0, I13.0, I13.2
		
2d	• Age ≥75 y	
Measured on the day of drug initiation
 
Age ≥75
		

Appendix A

2e	• Age ≥65 y and one of the following: – Diabetes mellitus on treatment	
Measured on the day of drug initiation
 
Age ≥65 +
 
Measured any time prior to and including day of drug initiation in any diagnosis position and inpatient or outpatient care setting
 
Diabetes mellitus
 
ICD-9 diagnosis: 250.x1, 250.x3, 250.x0, 250.x2 ICD-10 diagnosis: E10.x, E11.x
 
AND At least one of the following drug prescriptions from 0 to 30 days after diagnosis*:
 
Bolus Insulin: Insulin human regular, Insulin Aspart, Insulin Glulisine, Insulin Lispro, Insulin Aspart/Insulin Aspart Protamine, Insulin Lispro/Insulin Lispro Protamine, insulin.pork purified Basal Insulin: Insulin human isophane (NPH), Insulin human regular/ Insulin human isophane (NPH), Insulin Detemir, Insulin Glargine, Insulin Degludec, Insulin zinc human rec, Insulin zinc extend human rec, insulin nph human recom/insulin regular human rec, Insulin zinc human rec, Insulin nph human recom/insulin regular human rec
 
Metformin
 
DDP4 inhibitors : Alogliptin, Linagliptin, Saxagliptin, Sitagliptin
 
Sulfonylureas Acetohexamide, Chlorpropamide, tolazamide, tolbutamide, Glipizide, Glyburide, Glimepiride
 
Meglitinide derivatives Repaglinide, Nateglinide
 
Alpha-glucosidase inhibitors Acarbose, Miglitol
 
Thiazolidinediones (TZDs) Rosiglitazone, Pioglitazone
 
Glucagonlike peptide-1 (GLP-1) agonists Exenatide, Liraglutide, Lixisatide, Albiglutide, Dulaglutide, semaglutide
 
SGLT2 inhibitors Canagliflozin, Dapagliflozin, Empagliflozin, Erugliflozin
 
Pramlintide Pramlintide

	– Documented coronary artery disease (any of: prior myocardial infarction, positive stress test, positive nuclear perfusion study, prior CABG surgery or PCI, angiogram showing ≥75% stenosis in a major coronary artery	
Measured any time prior to and including day of drug initiation in diagnosis position and care setting specified below:
 
Acute MI (inpatient, any position): ICD-9 diagnosis: 410.xx Old MI (inpatient, any position): ICD-9 diagnosis: 412.xx Angina pectoris (inpatient, any position): ICD-9 diagnosis: 413.x Unstable angina (inpatient, any position): ICD-9 diagnosis: 411.x ICD-10 diagnosis: I24.1x, I20.0x, I25.1x, I25.7x, I24.0x, I24.8x, I24.9x –OR– CARG (inpatient, any position): CPT-4: 33510 – 33536, 33545, 33572 ICD-9 procedure: 36.1x, 36.2x –OR– –OR– Coronary revascularization (PTCA_stenting) (inpatient, any position): CPT-4: 92973, 92982, 92984, 92995, 92996, 92920 – 92921, 92924 – 92925, 92937, 92938, 92941, 92943, 92944 ICD-9 procedure: 00.66, 36.01, 36.02, 36.03, 36.05, 36.09 ICD-10 procedure: Coronary bypass in Coronary Revascularization sheet –OR– Stenting: Stenting in Coronary Revascularization sheet –OR– Transmyocardial revascularization: CPT-4: 33140, 33141 OR – Inpatient ICD-9 procedure: 36.31-36.34 ICD-10: 021K0Z, 021K4Z5, 021L0Z5, 021L4Z5, 02QA3ZZ, 02QB4ZZ, 02QB8ZZ, 02QC3ZZ, 02QC4ZZ

	– Hypertension requiring medical treatment	
Measured any time prior to and including day of drug initiation** in any diagnosis position and inpatient or outpatient care setting
 
Hypertension
 
ICD-9 diagnosis: 401.x – 405.x AND At least one drug prescriptions from 0 to 14 days after diagnosis*:
 
ACE inhibitor Benazepril, captopril, enalapril, fosinopril, lisinopril, moexipril, perindopril, quinapril, ramipril, trandolapril ARB Azilsartan, candesartan, eprosartan, irbesartan, losartan, olmesartan, telmisartan, valsartan Beta blocker Acebutolol, atenolol, betaxolol, bisoprolol, carteolol, carvedilol, esmolol, labetalol, metoprolol tartrate, metoprolol succinate, propranolol, pbenztol, pindolol, nadolol, nebivolol, sotalol, timolol Calcium channel blocker Diltiazem, mibepradil, verapamil, amlodipine, clevudipine, bepridil, felodipine, isradipine, nicardipine, nifedipine, nimodipine, nisoldipine Other hypertension drugs Doxazosin, eplerenone, prazosin, terazosin, clonidine, guanabenz, guanadrel, guanethidine, guanfacine, hydralazine, methyldopa, metyrosine, reserpine, minoxidil, aliskiren, apraclonidine

3	Age >18 y at entry	Measured on the day of drug initiation
4	Written, informed consent	N/A
	EXCLUSION CRITERIA	

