6.3.2 Study follow-up

Both as-treated (AT) and intention-to-treat (ITT) analyses will be conducted with treatment defined as the index drug on the day of cohort entry. Because adherence in the real-world databases is expected to be much worse than in the trial, the AT analysis is the **primary** analysis, as it targets the relative hazard of outcomes on treatment.

For the AT analyses, the follow-up will start the day after initiation of apixaban and comparator and will continue until the earliest date of the following events:

- The first occurrence of the outcome of interest, unless otherwise specified for selected outcomes,
- The date of end of continuous registration in the database,
- End of the study period,
- Measured death event occurs,

- Nursing home admission
 - Nursing home admissions are considered a censoring event because the data sources utilized typically provide little to no data on a patient, particularly on drug utilization, after admission. We will utilize this as an exclusion reason for cohorts for the same reason.
- The date of drug discontinuation, defined as the date of the last continuous treatment episode of the index drug (dabigatran and comparator) plus a defined grace period (i.e., 10 days after the end of the last prescription's days' supply in main analyses).
- The date of augmentation or switching from exposure to comparator or vice versa or augmentation/switching to any other NOAC (e.g. switching from dabigatran or warfarin to apixaban would be a censoring event);
 - A dosage change on the index treatment does not fulfill this criterion
 - An added treatment that is not part of the exposure or comparator group does not fulfill this criterion
- Dispensing of a fibrinolytic agent

For the intention-to-treat (ITT) analyses, the censoring based on the augmentation/switching and treatment discontinuation will be replaced with a maximum allowed follow-up time of 365 days.

7. Initial Feasibility Analysis

Action report name:

For dabigatran vs. warfarin

Optum- <https://bwh-dope.aetion.com/projects/details/707/results/59579/result/0>

Marketscan- <https://bwh-dope.aetion.com/projects/details/708/results/59601/result/0>

Medicare- <https://bwh-dope.aetion.com/projects/details/709/results/59602/result/0>

Date conducted: 10/5/20 (Medicare 10/6/20)

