Hyperthyroidism + Hypothyroidism + Other disorders of thyroid gland (for PS); n (%)	3,831 (16.9%)	479 (16.3%)	0.02	8,436 (12.4%)	1,861 (12.5%)	0.00	17,662 (13.0%)	3,549 (14.1%)	-0.03	29929 (13.2%)	5889 (13.7%)	-0.01
Delirium + Psychosis (for PS); n (%)	198 (0.9%)	29 (1.0%)	-0.01	1,554 (2.3%)	211 (1.4%)	0.07	1,839 (1.4%)	311 (1.2%)	0.02	3591 (1.3%)	551 (1.3%)	0.03
Any use of Meglitinides (for PS); n (%)	38 (0.2%)	3 (0.1%)	0.03	324 (0.5%)	74 (0.5%)	0.00	377 (0.3%)	74 (0.3%)	0.00	739 (0.3%)	151 (0.4%)	-0.02
Any use of AGIs (for PS); n (%)	17 (0.1%)	4 (0.1%)	0.00	69 (0.1%)	28 (0.2%)	-0.03	109 (0.1%)	30 (0.1%)	0.00	195 (0.1%)	62 (0.1%)	0.00
CKD stage 3-6 + dialysis (for PS); n (%)	4 (0.0%)	0 (0.0%)	#DIV/0!	0 (0.0%)	0 (0.0%)	#DIV/0!	0 (0.0%)	0 (0.0%)	#DIV/0!	0 (0.0%)	#VALUE!	#VALUE!
Use of thiazide-United; n (%)	2,786 (12.3%)	342 (11.6%)	0.02	7,453 (11.0%)	1,623 (10.9%)	0.00	16,971 (12.5%)	3,212 (12.7%)	-0.01	27210 (12.0%)	5177 (12.0%)	0.00
Use of betablockers; n (%)	13,713 (60.5%)	1,820 (62.0%)	-0.03	44,683 (65.9%)	10,110 (67.7%)	-0.04	87,512 (64.3%)	16,625 (65.9%)	-0.03	145908 (66.3%)	28555 (66.3%)	-0.04
Use of calcium channel blockers; n (%)	7,737 (34.1%)	1,075 (36.6%)	-0.05	24,743 (36.5%)	5,699 (38.2%)	-0.04	48,655 (35.8%)	9,878 (39.2%)	-0.07	81135 (35.8%)	16652 (38.6%)	-0.06
All antidiabetic medications except Insulin; n (%)	4,109 (18.1%)	615 (20.9%)	-0.07	12,310 (18.2%)	2,931 (19.6%)	-0.04	25,209 (18.5%)	5,082 (20.1%)	-0.04	41628 (18.4%)	8628 (20.0%)	-0.04
DM Medications - Insulin Copy; n (%)	864 (3.8%)	128 (4.4%)	-0.03	3,888 (5.7%)	795 (5.3%)	0.02	5,129 (3.8%)	926 (3.7%)	0.01	9881 (4.4%)	1849 (4.3%)	0.00
Use of Low Intensity Statins; n (%)	8,138 (35.9%)	964 (32.8%)	0.07	23,820 (35.1%)	4,901 (32.8%)	0.05	48,921 (35.9%)	8,854 (35.1%)	0.02	80879 (35.7%)	14719 (34.2%)	0.03
Use of High Intensity Statins; n (%)	4,085 (18.0%)	619 (21.1%)	-0.08	13,552 (20.0%)	3,233 (21.7%)	-0.04	26,998 (19.2%)	5,459 (21.6%)	-0.06	43735 (19.3%)	9311 (21.6%)	-0.06
Malignant hypertension; n (%)	693 (3.1%)	107 (3.6%)	-0.03	27,053 (39.9%)	6,491 (43.5%)	-0.07	16,757 (12.3%)	4,133 (16.4%)	-0.12	44503 (19.6%)	10731 (24.9%)	-0.13
Cardiovascular stress test; n (%)	58 (0.3%)	13 (0.4%)	-0.02	449 (0.7%)	69 (0.5%)	0.03	579 (0.4%)	107 (0.4%)	0.00	1086 (0.5%)	189 (0.4%)	0.01
Echocardiogram; n (%)	3,464 (15.3%)	835 (28.4%)	-0.32	23,390 (34.5%)	7,438 (49.8%)	-0.31	29,798 (21.9%)	9,331 (37.0%)	-0.34	56652 (25.0%)	17604 (40.8%)	-0.34
Number of BNP tests												

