Chronic kidney disease Stage 1-2 (for PS); n (%)	0 (0.0%)	0 (0.0%)	#DIV/0!	0 (0.0%)	0 (0.0%)	#DIV/0!	0	0	#VALUE!	#VALUE!	#VALUE!	#VALUE!
Chronic kidney disease Stage 3-6 (for PS); n (%)	0 (0.0%)	0 (0.0%)	#DIV/0!	0 (0.0%)	0 (0.0%)	#DIV/0!	0 (0.0%)	0 (0.0%)	#DIV/0!	0 (0.0%)	0 (0.0%)	#DIV/0!
Bladder stones+Kidney stones (for PS); n (%)	35 (1.3%)	35 (1.3%)	0.00	191 (1.4%)	229 (1.6%)	-0.02	283 (1.3%)	274 (1.2%)	0.01	509 (1.3%)	538 (1.4%)	-0.01
Diabetes with peripheral circulatory disorders+Gangrene+Osteomyelitis(for PS)v3 with ICD10 Copy; n (%)	75 (2.7%)	49 (1.8%)	0.06	285 (2.0%)	269 (1.9%)	0.01	408 (1.8%)	430 (1.9%)	-0.01	768 (2.0%)	748 (1.9%)	0.01
Alcohol abuse or dependence+Drug abuse or dependence (for PS); n (%)	0 (0.0%)	0 (0.0%)	#DIV/0!	0 (0.0%)	0 (0.0%)	#DIV/0!	0 (0.0%)	0 (0.0%)	#DIV/0!	0 (0.0%)	0 (0.0%)	#DIV/0!
Diabetes with other ophthalmic manifestations+Retinal detachment, vitreous hemorrhage, vitrectomy+Retinal laser coagulation therapy (for PS); n (%)	11 (0.4%)	11 (0.4%)	0.00	204 (1.5%)	168 (1.2%)	0.03	224 (1.0%)	191 (0.9%)	0.01	439 (1.1%)	370 (0.9%)	0.02
Other atherosclerosis+Cardiac conduction disorders+Other CVD (for PS)v2 Copy; n (%)	515 (18.5%)	505 (18.1%)	0.01	4,706 (33.7%)	4,661 (33.4%)	0.01	3,619 (16.2%)	3,549 (15.9%)	0.01	8840 (22.6%)	8715 (22.3%)	0.01
Previous cardiac procedure (CABG or PTCa or Stent) + History of CABG or PTCa (for PS)v3; n (%)	153 (5.5%)	141 (5.1%)	0.02	730 (5.2%)	700 (5.0%)	0.01	1,780 (8.0%)	1,772 (7.9%)	0.00	2663 (6.8%)	2613 (6.7%)	0.00
Hyperthyroidism +Hypothyroidism + Other disorders of thyroid gland (for PS); n (%)	430 (15.4%)	454 (16.3%)	-0.02	1,697 (12.2%)	1,748 (12.5%)	-0.01	3,078 (13.8%)	3,045 (13.6%)	0.01	5205 (13.3%)	5247 (13.4%)	0.00
Delirium + Psychosis (for PS); n (%)	28 (1.0%)	27 (1.0%)	0.00	190 (1.4%)	207 (1.5%)	-0.01	285 (1.3%)	264 (1.2%)	0.01	503 (1.3%)	498 (1.3%)	0.00
Any use of Meglitinides (for PS); n (%)	4 (0.1%)	3 (0.1%)	0.00	76 (0.5%)	69 (0.5%)	0.00	72 (0.3%)	57 (0.3%)	0.00	152 (0.4%)	129 (0.3%)	0.02
Any use of AGIs (for PS); n (%)	2 (0.1%)	4 (0.1%)	0.00	17 (0.1%)	27 (0.2%)	-0.03	18 (0.1%)	28 (0.1%)	0.00	37 (0.1%)	59 (0.2%)	-0.03
CKD stage 3-6 + dialysis (for PS); n (%)	1 (0.0%)	0 (0.0%)	#DIV/0!	0 (0.0%)	0 (0.0%)	#DIV/0!	0 (0.0%)	0 (0.0%)	#DIV/0!	1 (0.0%)	0 (0.0%)	#DIV/0!
Use of thiazide; n (%)	319 (11.4%)	332 (11.9%)	-0.02	1,447 (10.4%)	1,514 (10.8%)	-0.01	2,908 (13.0%)	2,867 (12.8%)	0.01	4674 (12.0%)	4713 (12.1%)	0.00

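### Inclusion 2e sets no visible index-date limit on the qualifying drug fill and omits thiazides from its antihypertensive list: a small cohort-definition point to close before analysis

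*Combined protocol and SAP*

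**What the plan says.** Criterion 2 in Appendix A is met by any one of 2a to 2e. Route 2d admits everyone aged 75 or over. Route 2e admits those aged 65 or over with treated diabetes, coronary artery disease or treated hypertension.

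- **Diabetes branch.** The diagnosis window is "Measured any time prior to and including day of drug initiation in any diagnosis position and inpatient or outpatient care setting". The treatment test is "At least one of the following drug prescriptions from 0 to 30 days after diagnosis".
- **Hypertension branch.** The diagnosis window is again "Measured any time prior to and including day of drug initiation". The treatment test is "At least one drug prescriptions from 0 to 14 days after diagnosis".
- **Markers.** Both fill windows end in an asterisk, and the hypertension diagnosis window carries a double asterisk. The text of these notes is not visible in the appendix.
- **Antihypertensive list.** It names ACE inhibitors, ARBs, beta blockers, calcium channel blockers and a last group: "Other hypertension drugs Doxazosin, eplerenone, prazosin, terazosin, clonidine, guanabenz, guanadrel, guanethidine, guanfacine, hydralazine, methyldopa, metyrosine, reserpine, minoxidil, aliskiren, apraclonidine". No thiazide appears in any group.
- **Coronary branch.** It requires no drug fill.

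Section 6.3.2 says that "the follow-up will start the day after initiation". Section 5.1 describes the stroke risk factors as present in the 12 months before the drug is started. Appendix B carries thiazide use as a covariate of its own, before matching ("Use of thiazide-United; n") and after it ("Use of thiazide; n").

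**The concern.** A new-user cohort should be fixed by what is known at the index date. In 2e the fill is timed from the diagnosis, and the diagnosis may be on the index day or shortly before it. Read literally, a fill up to 30 days (diabetes) or 14 days (hypertension) after index can complete eligibility, and it then falls inside follow-up.

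Such a patient has to be alive, enrolled and filling prescriptions on that later date. This is selection on post-baseline data, and it can act in either direction. An early death or disenrolment prevents the qualifying fill. An early non-fatal stroke followed by a new antihypertensive could create one. Propensity-score matching on baseline covariates does not remove this. The lower quartile of follow-up in Section 9 is about 38 days, so a 30-day window covers much of the early on-treatment time.

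The thiazide gap is a separate misclassification. The criterion is meant to identify hypertension that needs drug treatment, yet a patient treated only with a thiazide does not register as treated.

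**Working it through.** **Who can be affected.** Patients aged 75 or over enter by 2d as defined in Appendix A, and those under 65 cannot use 2e. That leaves ages 65-74. From the pooled columns of the matched table in Appendix B:

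- 10,193 (warfarin) + 10,247 (dabigatran) = 20,440
- 20,440 / 78,140 = 26.2%

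This is a ceiling, because many of these patients will have entered by 2a-2c, through coronary disease, or through a fill before index. A post-index fill decides entry only if all of these hold:

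1. age 65-74;
2. none of 2a-2c and no coronary disease;
3. a diabetes diagnosis within 30 days, or a hypertension diagnosis within 14 days, up to and including index;
4. no earlier diagnosis-fill pair in the available history.

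**Size of the post-index part.** The documents do not count these patients. Assume that 1-5% of the age band depended on a post-index fill:

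- 1%: 204 patients; 204 / 78,140 = 0.26%
- 5%: 1,022 patients; 1,022 / 78,140 = 1.31%

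Set the fill window against the 98-day median follow-up in Section 9, taking events as evenly spread and the age band as having the cohort's average risk and follow-up:

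- low end, 14-day window: 14/98 × 0.26% = 0.04% of events
- high end, 30-day window: 30/98 × 1.31% = 0.4% of events

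Of about 441 expected events that is roughly 0.2 to 1.8.

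**The plan's nearest figure.** Section 10 gives no number for 2e, but its pooled power depends on cohort size and reproduces. Events = 78,140 × 5.64/1,000 = 440.71. With 1:1 allocation, power = Φ(½√events × |ln HR| − 1.96). This gives 0.9918 at HR 0.66 and 0.9779 at the margin of 1.46, both as stated. Removing a share of the 20,440 gives:

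| Share removed | Patients left | Events | Power, superiority | Power, non-inferiority |
|---|---|---|---|---|
| 1% | 77,936 | 439.6 | 0.992 | 0.978 |
| 5% | 77,118 | 434.9 | 0.991 | 0.976 |
| 20% | 74,052 | 417.7 | 0.989 | 0.972 |
| all | 57,700 | 325.4 | 0.963 | 0.927 |

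Power is therefore not the issue. What remains is selection, which power does not measure.

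**Thiazides.** Matched users number 4,674 + 4,713 = 9,387, and 9,387 / 78,140 = 12.0%. This shows that the class is already coded; it does not count wrong exclusions. The flowchart step for 2a-2e in Section 5.3 removed 11,313 + 17,737 + 24,940 = 53,990 of 64,158 + 121,406 + 324,258 = 509,822 patients (10.6%). Patients treated only by a thiazide are an uncounted part of those 53,990.

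**The case against.** The strongest reply is that the plan may already limit the window. The asterisks sit on exactly the wording at issue, and Appendix A refers readers to a separate folder for further detail. Each entry also opens with a look-back that ends on the day of initiation, which can be read as governing diagnosis and fill together. Section 5.1 fits that reading. This stands as far as it goes: a reader might infer that entry was in fact partly decided by the future, and the documents do not show it. They show wording that permits it.

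A reader might also infer classic immortal time, with patients having to stay event-free until the fill. The text does not require that. Someone with a non-fatal stroke on day 5 and a fill on day 10 meets it. The rule is the same in both arms, and nothing in the documents establishes an effect on the hazard ratio.

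A decisive post-index fill should also be uncommon. Matched patients have a pooled mean of about 1,368 prior days in the database, and median baseline days on antihypertensives are 169-173 in every matched arm. These figures cover all ages, but they describe mostly long-observed, already treated patients.

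On thiazides, it would be wrong to read the 12.0% as the share misclassified. It is any thiazide use, at all ages, among patients already admitted. Other listed classes are common (beta blockers 66%, calcium channel blockers 38-39%, ACE inhibitors 35%), and a thiazide user who also fills one of these within the window still qualifies.

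What none of this answers is that the visible rule states no limit at index, that its look-back differs from Section 5.1, and that the list omits a class measured elsewhere in the plan.

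**Conclusion.** Two small defects of definition stand. First, 2e as visible lets a fill after the start of follow-up complete eligibility for a narrow group aged 65-74; actual use of post-index data is possible but not demonstrated. Second, the antihypertensive list wrongly excludes patients aged 65-74 whose hypertension is treated only by a thiazide and who have no other route in 2a-2e. Their number cannot be obtained from the documents.

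The ceiling on the first defect is the 26.2% of matched patients in the age band. The estimates of 0.3-1.3% of patients and 0.04-0.4% of events rest entirely on the assumed 1-5%, which has no source in the plan. The second defect narrows the cohort, and no bias in the treatment comparison is shown from it. Neither would be expected to change the study's conclusion. Both are worth correcting because they are cheap and leave the entry rule open to different implementations.

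**What to change.** - State in both drug-fill branches of 2e that the diagnosis and the qualifying fill must be dated on or before the index date, or print the note that already says so.
- Reconcile the look-back in 2e (all available history) with Section 5.1 (12 months).
- Add the thiazide class, already coded for Appendix B, to the antihypertensive list.
- Re-run the 2a-2e step of the flowchart and report, by arm and database, how many patients enter only through 2e.

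The cost is about one line per criterion and one re-run of cohort assembly. Counts will shift slightly, and the match, Table 1 and the Section 10 power tables need refreshing to agree. Section 13 carries no date for the comparative analyses, so on the face of the document the change can still be made before outcomes are compared.
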